7.2 Evaluation of Safety

Analyses will be performed for all patients having received at least one dose of study drug. The study will use the CTCAE v4.0 for reporting of non-hematologic adverse events and modified criteria for hematologic adverse events, see Appendix 2.

The Principal Investigator at the UCSF Coordinating Center will hold the role of Study Chair. The Study Chair is responsible for the overall conduct of the study and for monitoring its safety and progress at all participating sites.

7.3 **Definitions of Adverse Events**

7.3.1 Adverse Event

An adverse event (also known as an adverse experience) is defined as any untoward medical occurrence associated with the use of a drug in humans, whether or not considered drug related. More specifically, an adverse event (can be any unfavorable and unintended sign (e.g., an abnormal laboratory finding), symptom, or disease temporally associated with the use of a drug, without any judgment about causality. An adverse event can arise from any use of the drug (e.g., off-label use, use in combination with another drug) and from any route of administration, formulation, or dose, including an overdose.

7.3.2 Adverse Reaction

An adverse reaction is defined as any adverse event caused by the use of a drug. Adverse reactions are a subset of all suspected adverse reactions for which there is reason to conclude that the drug caused the event.

7.3.2.1 Suspected

A suspected adverse reaction is defined as any adverse event for which there is a reasonable possibility that the drug caused the adverse event. For the purposes of IND safety reporting,

Phase 2 - Ruxolitinib Page 44 of 67

"reasonable possibility" indicates that there is evidence to suggest a causal relationship between the drug and the adverse event. A suspected adverse reaction implies a lesser degree of certainty about causality than an adverse reaction.

7.3.2.2 Unexpected

An adverse event or suspected adverse reaction is considered *unexpected* if it is not listed in the investigator brochure or package insert(s), or is not listed at the specificity or severity that has been observed, or, if an investigator brochure is not required or available, is not consistent with the risk information described in the general investigational plan or elsewhere in the current application.

"Unexpected," as used in this definition, also refers to adverse events or suspected adverse reactions that are mentioned in the investigator brochure as occurring with a class of drugs or as anticipated from the pharmacological properties of the drug, but are not specifically mentioned as occurring with the particular drug under investigation.

Adverse events that would be anticipated to occur as part of the disease process are considered *unexpected* for the purposes of reporting because they would not be listed in the investigator brochure. For example, a certain number of non-acute deaths in a cancer trial would be anticipated as an outcome of the underlying disease, but such deaths would generally not be listed as a suspected adverse reaction in the investigator brochure.

Some adverse events are listed in the Investigator Brochure as occurring with the same class of drugs, or as anticipated from the pharmacological properties of the drug, even though they have not been observed with the drug under investigation. Such events would be considered *unexpected* until they have been observed with the drug under investigation. For example, although angioedema is anticipated to occur in some patients exposed to drugs in the ACE inhibitor class and angioedema would be described in the investigator brochure as a class effect, the first case of angioedema observed with the drug under investigation should be considered *unexpected* for reporting purposes.

7.3.2.3 **Serious**

An adverse event or suspected adverse reaction is considered *serious* if, in the view of either the investigator or sponsor, it results in any of the following outcomes:

- Death
- Life-threatening adverse event
- Inpatient hospitalization or prolongation of existing hospitalization
- A persistent or significant incapacity or substantial disruption of the ability to conduct normal life function
- Congenital anomaly/birth defect

Important medical events that may not result in death, are life threatening, or require hospitalization may be considered serious when, based upon appropriate medical judgment, they may jeopardize the patient or participant and may require medical or surgical intervention to prevent one of the outcomes listed in this definition. Examples of such medical events include allergic bronchospasm requiring intensive treatment in an emergency room or at home, blood dyscrasias or convulsions that do not result in inpatient hospitalization, or the development of drug dependency or drug abuse.

Phase 2 - Ruxolitinib Page 45 of 67

Version date: 03-22-2023 Protocol CC# 16201

- In the event of a serious adverse event, the PI, the institutional review board (per institutional reporting requirements), and Incyte Corporation will be notified using the FDA Form 3500 MedWatch report. All events meeting the definition of a serious adverse event should be recorded on a MedWatch 3500 Form (http://www.fda.gov/downloads/AboutFDA/ReportsManualsForms/Forms/UCM163919.p df) and submitted to:DSMC
- 2. Local IRB per institutional reporting requirements
- 3. FDA
- 4. Incyte
- In addition to completing appropriate patient demographic and suspect medication information, the report should include as applicable the following information that is available at the time of report within the Event Description (section 5) of the MedWatch 3500 form:CTCAE term(s) and grade(s)
- Current status of study drug
- All interventions to address the AE (testing and result, treatment and response)
- Hospitalization and/or discharge dates
- Event relationship to study drug

7.3.2.4 Life-threatening

An adverse event or suspected adverse reaction is considered *life threatening* if, in the view of either the investigator or sponsor, its occurrence places the patient or participant at immediate risk of death. It does not include an adverse event or suspected adverse reaction that, had it occurred in a more severe form, might have caused death.

7.4 Recording of an Adverse Event

All grade 3 and above adverse events will be entered into OnCore[®], whether or not the event is believed to be associated with use of the study drug. Data about these events and their severity will be recorded using the NCI CTCAE v4.0.

The Investigator will assign attribution of the possible association of the event with use of the investigational drug, and this information will be entered into OnCore® using the classification system listed below:

Relationship	Attribution	Description	
Unrelated to investigational	Unrelated	The AE is clearly NOT related to the intervention	
drug/intervention	Unlikely	The AE is doubtfully related to the intervention	
Deleted to investigational	Possible	The AE may be related to the intervention	
Related to investigational drug/intervention	Probable	The AE is likely related to the intervention	
	Definite	The AE is clearly related to the intervention	

Signs or symptoms reported as adverse events will be graded and recorded by the Investigator according to the CTCAE. When specific adverse events are not listed in the CTCAE, they will be graded by the Investigator as *none*, *mild*, *moderate* or *severe* according to the following grades and definitions:

Phase 2 - Ruxolitinib Page 46 of 67

Grade 0	No AE (or within normal limits)
Grade 1	Mild; asymptomatic or mild symptoms; clinical or diagnostic observations only; intervention not indicated
Grade 2	Moderate; minimal, local, or noninvasive intervention (e.g., packing, cautery) indicated; limiting age-appropriate instrumental activities of daily living (ADL)
Grade 3:	Severe or medically significant but not immediately life-threatening; hospitalization or prolongation of hospitalization indicated; disabling; limiting self-care ADL
Grade 4:	Life-threatening consequences; urgent intervention indicated
Grade 5:	Death related to AE

7.5 Follow-up of Adverse Events

All adverse events will be followed with appropriate medical management until resolved. Patients removed from study for unacceptable adverse events will be followed until resolution or stabilization of the adverse event. For selected adverse events for which administration of the investigational drug was stopped, a re-challenge of the participant with the investigational drug may be conducted if considered both safe and ethical by the Investigator.

Follow-up Reports:

Additional information may be added to a previously submitted report by adding to the original MedWatch 3500 report and submitting it as follow-up or creating supplemental summary information and submitting it as follow-up with the original MedWatch 3500 form.

7.6 Adverse Events Monitoring

All adverse events, whether or not unexpected, and whether or not considered to be associated with the use of the study drug, will be entered into OnCore[®], as noted above.

The Investigator will assess all adverse events and determine reportability requirements to the UCSF Data and Safety Monitoring Committee (DSMC) and UCSF's Institutional Review Board, the Institutional Review Board (IRB); and, when the study is conducted under an Investigational New Drug Application (IND), to the Food and Drug Administration (FDA) if it meets the FDA reporting criteria.

All adverse events entered into OnCore® will be reviewed by the Helen Diller Family Comprehensive Cancer Center Site Committee on a weekly basis. The Site Committee will review and discuss at each weekly meeting the selected toxicity, the toxicity grade, and the attribution of relationship of the adverse event to the administration of the study drug(s).

All grade(s) 3-5 adverse events entered into OnCore® will be reviewed on a monthly basis at the Site Committee meetings. The Site Committee will review and discuss the selected toxicity, the toxicity grade, and the attribution of relationship of the adverse event to the administration of the study drug(s).

In addition, all suspected adverse reactions considered "serious" entered into OnCore®, will be reviewed and monitored by the Data and Safety Monitoring Committee on an ongoing basis and discussed at DSMC meetings, which take place every six weeks.

Phase 2 - Ruxolitinib Page 47 of 67

Protocol CC# 16201

For a detailed description of the Data and Safety Monitoring Plan for a Multicenter Phase 2 or 3 Institutional Study at the Helen Diller Comprehensive Cancer Center please refer Appendix 2.

7.7 Expedited Reporting

Reporting to the Data and Safety Monitoring Committee

If a death occurs during the treatment phase of the study or within 30 days after the last administration of the study drug(s) and it is determined to be related either to the study drug(s) or to a study procedure, the Investigator or his/her designee must notify the DSMC Chair (or qualified alternate) within 1 business day of knowledge of the event. The contact may be by phone or e-mail.

Reporting to UCSF Institutional Review Board (Institutional Review Board)

The Principal Investigator must report events meeting the UCSF IRB definition of "Unanticipated Problem" (UP) within 5 business days of his/her awareness of the event.

Expedited Reporting to the Food and Drug Administration

If the study is being conducted under an IND, the Sponsor-Investigator is responsible for determining whether or not the suspected adverse reaction meets the criteria for expedited reporting in accordance with Federal Regulations (21 CFR §312.32).

The Investigator must report in an IND safety report any suspected adverse reaction that is both serious and unexpected. The Sponsor-Investigator needs to ensure that the event meets all three definitions:

- Suspected adverse reaction
- Unexpected
- Serious

If the adverse event does not meet all three of the definitions, it should not be submitted as an expedited IND safety report.

The timeline for submitting an IND safety report to FDA is no later than **15 calendar days** after the Investigator determines that the suspected adverse reaction qualifies for reporting (21 CFR 312.32(c)(1)).

Any unexpected fatal or life-threatening suspected adverse reaction will be reported to FDA no later than **7 calendar days** after the Investigator's initial receipt of the information (21 CFR 312.32(c)(2)).

Any relevant additional information that pertains to a previously submitted IND safety report will be submitted to FDA as a Follow-up IND Safety Report without delay, as soon as the information is available (21 CFR 312.32(d)(2)).

Reporting to Pharmaceutical Companies providing Study Drug

Incyte Corporation, Adverse Events Reporting (within 24 hours of learning of the SAE):

[contact]

Phase 2 - Ruxolitinib Page 48 of 67

Version date: 03-22-2023 Protocol CC# 16201

8 Statistical Considerations and Evaluation of Results

8.1 Study Endpoints

This is a phase II open label study to identify baseline and/or pharmacodynamics biomarkers of clinical response to ruxolitinib based on quantitative change in tumor size following 14-21 days of neoadjuvant ruxolitinib in patients with operable HNSCC. Clinical response will be defined by the change of the Δ Tumor size between two measurements during study windows.

8.2 Determination of Sample Size and Accrual Rate

8.2.1 Sample Size and Power Estimate

The primary objective of the study is to identify baseline and/or pharmacodynamic biomarkers that might have predictive utility to determine the clinical response to ruxolitinib. As a biomarker study, the statistical design is to accrue a sufficient number of patients and provide 80% power to test one or any of 5 key hypotheses with a shared alpha of 0.15: 1) relationship between clinical response (ΔTumor size) and baseline STAT activation (pSTAT3 expression); 2) relationship between clinical response (ΔTumor size) and change in expression of pSTAT3; 3) relationship between responders (ΔTumor size) and change in expression of cyclin D1: 4) relationship between clinical response (ΔTumor size) and baseline genetic or epigenetic PTPRT or PTPRD silencing; 5) relationship between responders (ΔTumor size) and baseline C-reactive protein. An overall alpha of .15 will be shared equally among the five primary hypotheses. 23 patients with complete biomarker data are needed to achieve 80% power for the 5 primary hypothesis and limit overall family wise error rate (FWER) to 15%. As estimated from our prior window trials, accounting for treatment compliance and quality paired tumor specimens, this will require enrollment of 45 patients. For each biomarker (baseline pSTAT3 expression, change from baseline of pSTAT3 expression, change from baseline of cycline D1 expression, baseline PTPRT or PTPRD silencing and baseline C-reactive protein), mean and standard deviation will be estimated and compared for significance between clinical responders and non-responders of ruxolitinib therapy using Wilcoxon rank tests. Our experience with our phase 0 clinical trial testing the STAT3 decoy also showed correlations between ΔKi-67 (the primary pharmacodynamic efficacy endpoint) and STAT3-target genes falling in the range of .50 to .67. Twenty-five patients will enable a two -tailed Spearman Correlation test at alpha = .03 to detect a true correlation of .56. For the expected 30% of patients with a PTPR mutation, a one-tailed Wilcoxon test will demonstrate increased sensitivity to ruxolitinib via a decrease in tumor size equal to 1.3 standard deviations with 23 patients (8 with a mutation).

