1.4.2 Additional Analysis

To determine if expression of serum proteins or DNA polymorphisms predict response to ruxolitinib targeting, paired serum (baseline, post-treatment) and baseline peripheral blood mononuclear cells (PBMCs) will be isolated. Blood will be processed for serum and isolation of PBMCs. Serum will be analyzed for proteomic markers using mass spectroscopy and luminex ELISA assays. DNA will be isolated from PBMC samples for SNP analysis. Tissue will be processed for DNA, fluorescence in situ hybridization (FISH), tissue microarrays, and

Phase 2 - Ruxolitinib Page 22 of 67

immunohistochemistry microarrays. Both uniplex and multiplex serum cytokine profile analysis, for correlation with other biomarkers and clinical responsiveness will be performed. For specific cytokines of interest, including IL-6, ELISA kits will be used. For multiplex analysis, the technology developed by Luminex Corporation (Austin, TX, http://www.luminexcorp.com) will be used. It enables a laboratory to simultaneously measure up to 100 analytes in a single microplate well, using very small sample volumes (less than 50 microliters). Previous studies have shown that a multi-marker panel offering the highest diagnostic power was comprised of 22 biomarkers, including EGF, EGFR, Cyfra 21-1, AFP, IL-8, MMP-3, CA 72-4, CA 15-3, MMP-2, TNF-RI, IL-7, HCGb, MIF, Mesothelin, MCP-1, IL-1Ra, FGFb, CEA, sVCAM-1, tPAI 1, RANTES, IGFBP-1. Statistical analysis using our novel ADE algorithm resulted in a sensitivity of 84.5%, specificity of 98%, and 92% of patients with active head and neck cancer correctly classified from a cross-validation serum set³⁶. Further proteomic analysis will be performed using IHC microarrays.

2 Objectives of the Study

2.1 **Primary Objective**

To identify baseline and/or pharmacodynamic biomarkers of response to ruxolitinib based upon association with quantitative change in tumor size (ΔTumor size) following 14-21 days of neoadjuvant ruxolitinib in patients with operable HNSCC. We hypothesize that ΔTumor size will correlate with five prioritized, predictive biomarkers which will be designated for specialized alpha spending: 1) baseline expression of pSTAT3; 2) change in expression of pSTAT3; 3) change in expression of the STAT3 target gene cyclin D1; 4) baseline silencing of protein tyrosine phosphatase receptors D or T (PTPRD or PTPRT) by mutation or methylation; 5) baseline elevation in peripheral inflammatory markers (C-reactive protein [CRP]).

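### The equal .03 split across the five primary tests is valid, but Holm's step-down procedure meets the same 15% familywise error and never declares fewer markers

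*Combined protocol and SAP*

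**What the plan says.** Section 2.1 names five markers whose relation to tumor change is the primary question. It says that tumor change "will correlate with five prioritized, predictive biomarkers which will be designated for specialized alpha spending". Section 8.2.1 gives the allocation: "An overall alpha of .15 will be shared equally among the five primary hypotheses". The stated purpose is to "limit overall family wise error rate (FWER) to 15"%. No step-down or alpha-recycling rule for these five tests appears anywhere.

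The power target is worded in two ways in 8.2.1. One aims to "provide 80% power to test one or any of 5 key hypotheses with a shared alpha of 0.15". The other says that "23 patients with complete biomarker data are needed to achieve 80% power for the 5 primary hypothesis". The sizing examples are:

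- "Twenty-five patients will enable a two -tailed Spearman Correlation test at alpha = .03 to detect a true correlation of .56"
- on the PTPR comparison, where the mutated group is taken to number 8: "a one-tailed Wilcoxon test will demonstrate increased sensitivity to ruxolitinib via a decrease in tumor size equal to 1.3 standard deviations with 23 patients"

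Section 8.4.2 lists five primary Spearman analyses and gives neither a significance level nor a multiplicity step. The Benjamini-Hochberg adjustment in 2.3.2 covers the paired pre- and post-treatment panel, not these five tests.

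**The concern.** The trial's main product is the list of markers declared to be associated with response. A fixed .03 per test spends the full 15% only when all five markers are null. If m0 of the five are null, the split's familywise error is at most m0 × .03, so part of the allowance goes unused once some markers are real. A real second, third, fourth or fifth marker then faces a stricter threshold than the plan's own error criterion requires. With 45 patients enrolled to obtain 23 evaluable ones, power given up in this way is costly to recover by other means.

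**Working it through.** **Inputs.** From 8.2.1: familywise alpha .15, five tests, two-tailed Spearman, correlation .56, 23 evaluable patients (25 in the Spearman example), and 8 of 23 with a mutation. Not in the documents, and so assumed: how many of the five markers are real, and how they correlate with each other.

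**The plan's own figures.**

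- Per-test alpha: .15/5 = .03. If the tests were independent, the familywise error would be 1 − .97^5 = .141.
- Spearman by Fisher's z: power = Φ(atanh(.56)·√(n−3) − z(.985)). At n = 25: .6328 × 4.690 − 2.170 = .798, so power is .788. The n for 80% is 3 + ((2.170 + .842)/.6328)² = 25.6. The stated 25 is reproduced to within rounding. At n = 23 the formula gives .745.
- Wilcoxon, 8 versus 15, shift 1.3 SD, one-tailed .03 (alpha assumed from the equal split): exact-test power .802.

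**Holm's thresholds.** Order the p-values from smallest to largest and compare them in turn with .15/5 = .03, .15/4 = .0375, .15/3 = .05, .15/2 = .075 and .15, stopping at the first failure.

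**Why the familywise error holds.** When the first true null is rejected, all m0 true nulls are still in play, so its threshold is at most .15/m0. The union bound gives m0 × .15/m0 = .15, with no condition on dependence. Every threshold is at least .03, so whatever the split rejects Holm also rejects. The argument needs only valid p-values; binary markers and mixed one- and two-tailed tests do not affect it.

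**Size of the gain.** Simulation: 40,000 trials per row, n = 23, Spearman p by the t approximation, latent correlation .56, markers independent given tumor change, both rules applied to the same data.

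| Real markers | Power per real marker, split → Holm | All real markers found, split → Holm |
|---|---|---|
| 1 | .694 → .698 | .694 → .698 |
| 2 | .688 → .714 | .490 → .539 |
| 3 | .691 → .744 | .364 → .481 |
| 4 | .691 → .778 | .276 → .481 |
| 5 | .691 → .825 | .213 → .566 |

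A separate run put the two-marker Holm figure at .72. The .69 lies below the Fisher-z .745 because a latent normal correlation of .56 gives a somewhat weaker rank correlation.

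**What does not change.** Holm's first threshold is also .03. The chance of at least one rejection is identical under both rules: about .73, .90, .96, .98 and .99 with one to five real markers.

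**What gets worse, within the limit.** A null marker's own false-positive rate goes from .031 to .048 (two real), .064 (three) and .101 (four). Familywise error goes from .091 to .129, .061 to .117 and .031 to .101. With no real markers it is the same under both rules, just under .15.

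**Sensitivity.**

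- Residual correlation .5 among markers: five real, .69 → .80; three real, .69 → .74.
- Correlation .40: two real, .357 → .374; three real, .350 → .382. At .30 with three real the gain is about 1.4 points.
- One marker binary with 8 of 23 positive: five real, .65 → .78; three real, .62 → .66.

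**The case against.** The strongest reply is that nothing here is wrong. The split is valid, simple and consistent with the .03 used for sizing. A reader might infer from the comparison with Holm that the plan contains a multiplicity error; it does not.

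A reader might also infer that the split has no merit of its own. That goes too far. It holds every null marker's false-positive rate at about .03, and Holm does not. With four real markers, about 9 points of power come with roughly a threefold rise in the chance of wrongly declaring the fifth. A team that wanted a per-marker cap could defend the split, particularly as 15% is already lenient. But 8.2.1 states its criterion as familywise error, and Holm meets that criterion.

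The gain is also easy to overstate. The 13-point figure needs all five markers real at .56. Section 2.1 does hypothesize all five, but the supporting range of .50 to .67 in 8.2.1 concerns correlations with ΔKi-67, not tumor size. The markers are also unlikely to be independent: cyclin D1 is a STAT3 target, and section 1.3 links PTPR mutation to raised pSTAT3. These points limit the size of the gain, not its direction.

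Finally, Holm needs one defined p-value per hypothesis, and for PTPRT/PTPRD the plan does not yet supply one. That stands, and the fix has to cover it.

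**Conclusion.** The point holds as an efficiency gain that the plan's own error criterion allows. That Holm never rejects fewer hypotheses and keeps the 15% limit is a mathematical result and rests on no simulation assumption. The size does depend on assumptions. At n = 23 and a correlation of .56, Holm adds about 0.4 points of power per real marker if one marker is real, about 2.5 if two, 5 if three, 9 if four and 13 if five (11 with residual correlation .5). At a correlation of .40 it adds only about 2 to 3 points with two or three real.

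The documents do not support a claim that Holm would reduce the sample size or raise the chance of finding at least one marker: on the one-or-any criterion nothing changes. The gain bears on the other wording, 80% power for the five hypotheses. Even there, at n = 23 and .56, Holm's simulated average reaches 80% only when all five markers are real. The accepted cost is the loss of the .03 cap on each individual null marker.

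**What to change.** In 8.2.1, replace the allocation sentence with: *The five primary p-values, one prespecified test per hypothesis, will be tested by the Holm step-down procedure at familywise alpha .15.* Keep .03 as the planning level, since it is Holm's first threshold.

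In 8.4.2, add that Holm-adjusted p-values will be reported for the five primary tests. For the i-th smallest p-value, the adjusted value is the largest of min(1, (6 − j)·p(j)) over j ≤ i; a marker is declared if this is at most .15.

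Before that, settle which single PTPRT/PTPRD p-value enters the procedure. Section 8.2.1 sizes a one-tailed Wilcoxon test by mutation status, while 8.4.2 makes a Spearman test of genetic or epigenetic silencing primary and states no sidedness. The two must be reconciled in the text.

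The cost is two sentences and the amendment route in 9.4 (Protocol Review Committee and IRB approval). Because the study is open label and the change loosens later thresholds, it should be dated before any biomarker-outcome analysis. Sample size and data collection are unaffected. Simultaneous confidence intervals that match Holm are less simple, but the plan specifies none for the five correlations.

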Endometrioid	32.30%	(80/248)		
Lung Adenocarcinoma	46.50%	(107/230)		
Lung Squamous	45.40%	(83/183)		
Ovary	14.30%	(65/456)		
Prostate	8.40%	(7/83)		
Stomach	53.60%	(81/151)		

STAT3 phosphorylation and suppressed the growth of human solid tumor xenografts with constitutive STAT3 activity. 10 Moreover, a strategy for patient selection is emerging. While activating mutations in JAK or STAT3 are not found in HNSCC, our recent comprehensive mutational profiling of HNSCC detected mutations in the PTPR family of genes in nearly one-third of tumors.27 Analysis of the 347 HNSCC tumors sequenced to date under the auspices of The Cancer Genome Atlas (TCGA) and our group. confirmed this high incidence of PTPR mutations (104/347, 30%). Further analysis demonstrated that

PTPR genes are mutated in a wide array of solid tumors sequenced to date under the auspices of the TCGA (see Table 1). Loss of function mutations in PTPRT and PTPRD lead to increased STAT3 phosphorylation, suggesting a tumor suppressor role. 30,31 Whole exome sequencing (n=374) and reverse-phase protein array data has been analyzed from 212 HNSCC tumors32. PTPR mutations were common and were associated with significantly increased phospho-STAT3 expression. Expression of PTPRT mutant proteins induced STAT3 phosphorylation and cell survival, consistent with an oncogenic "driver" phenotype. Computational modeling revealed functional consequences of PTPRT mutations on phosphor-tyrosine-substrate interactions. In addition to genomic aberrations, PTPRT is commonly methylated in HNSCC tumors (60%, 166/279 tumors analyzed to date in the TCGA); expression levels of PTPRT are significantly lower in these methylated tumors. Thus, silencing of key PTPR family genes may underlie STAT3 hyperactivation in HNSCC and other solid tumors. Identification and functional classification of these common genetic and epigenetic PTPR aberrations may permit companion biomarker development to select patients most likely to benefit from JAK inhibitors.

Phase 2 - Ruxolitinib Page 18 of 67

Figure 4: Decrease in pSTAT3_{Tyr705} expression with increase in concentration of Ruxolitinib

[figure not shown]

[figure not shown]
Figure 4. Cal 33 cells were treated with increasing concentrations of Ruxolitinib. After 24h, cells were harvested to obtain cell lysates. Forty micrograms of protein/lane were subjected to electrophoresis and immunoblotted for pSTAT3_{Tyr705} and total STAT3. B-tubulin was used as a loading control.

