- (4) Primary analysis using Spearman correlation between baseline genetic or epigenetic PTPRT/PTPRD silencing and %Change in tumor size will also be performed. As a supportive exploratory analysis, for clinical responders of patients who have achieved a 35% or greater on reduction in Δtumor size from baseline, descriptive statistics with mean, standard deviation and 95% CI will be calculated for baseline genetic or epigenetic PTPRT/PTPRD silencing and Wilcoxon rank tests will be used to determine the significant difference on baseline genetic or epigenetic PTPRT/PTPRD silencing between responders and non-responders.
- (5) Primary analysis using Spearman correlation between baseline C-reactive protein level and %Change in tumor size will also be performed. As a supportive exploratory analysis, for clinical responders of patients who have achieved a 35% or greater on reduction in Δtumor size from baseline, descriptive statistics with mean, standard deviation and 95% CI will be calculated for baseline C-reactive protein level and Wilcoxon rank tests will be used to determine the significant difference on baseline C-reactive protein level between responders and non-responders.

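### The 80% power claimed at 23 patients for all five primary hypotheses is not supported: the correlation figure is for 25 patients, and the PTPR figure is for another marker and a one-tailed test

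*Combined protocol and SAP*

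**What the plan says.** All of the sample size argument is in section 8.2.1.

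- **Overall claim.** "23 patients with complete biomarker data are needed to achieve 80% power for the 5 primary hypothesis". Earlier in the paragraph the aim is put more loosely: "provide 80% power to test one or any of 5 key hypotheses with a shared alpha of 0.15".
- **Alpha.** "An overall alpha of .15 will be shared equally among the five primary hypotheses", so .03 per hypothesis.
- **Correlation calculation.** "Twenty-five patients will enable a two -tailed Spearman Correlation test at alpha = .03 to detect a true correlation of .56". The effect size is motivated by an earlier phase 0 trial, with correlations between change in Ki-67 and "STAT3-target genes falling in the range of .50 to .67".
- **PTPR calculation.** "For the expected 30% of patients with a PTPR mutation, a one-tailed Wilcoxon test" is said to detect a 1.3 SD difference in tumor size change with 23 patients, 8 of them mutated.

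The target is 23 in the abstract, in section 3.2 and in the replacement policy (8.2.2). Section 8.4.2 makes Spearman correlation the primary analysis for all five markers. For the fourth it reads: "Primary analysis using Spearman correlation between baseline genetic or epigenetic PTPRT/PTPRD silencing". Section 2.1 also defines that marker as silencing by mutation or methylation. Section 1.3 reports that "PTPRT is commonly methylated in HNSCC tumors (60%, 166/279 tumors analyzed to date in the TCGA").

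**The concern.** Neither supporting calculation matches what it is meant to support. The Spearman calculation is the only one that applies to the four continuous markers, and it uses two patients more than the plan requires. The PTPR calculation differs from hypothesis 4 in its marker (mutation alone), its named test (Wilcoxon) and its sidedness (one-tailed). It also assumes 8 mutated patients, 35% of 23, although 30% of 23 is 6.9.

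The power statement is the only justification for 23 evaluable patients. If it is too high, a null result for a prioritized biomarker will be read as stronger evidence of no association than it is. For hypothesis 4, no stated figure describes the marker being tested. Leaving the sidedness of a primary test open also leaves a choice that could be made after the data are seen.

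**Working it through.** **Inputs.** From 8.2.1: alpha .15/5 = .03, true correlation .56 two-tailed, n = 25 or 23, shift 1.3 SD, 8 v 15, one-tailed. From 1.3: PTPR mutation 30%, PTPRT methylation 60%. Two assumptions are needed because the sentences do not repeat them: the PTPR test also uses alpha .03, and the correlation calculation also targets 80%.

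**1. Correlation.** Power = Φ(atanh(ρ)·√((n−3)/v) − z), with z = 2.170 for two-sided .03. Here v = 1 is the ordinary Fisher z formula and v = 1.06 is a usual Spearman correction. atanh(.56) = 0.633.

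- Plan's own case, n = 25, v = 1: 0.633 × √22 − 2.170 = 0.80, power **78.8%**. So .56 belongs with 25. With v = 1.06 it is 76.2%.
- Required number, n = 23, v = 1: 0.633 × √20 − 2.170 = 0.66, power **74.5%**. With v = 1.06: **71.9%**. The more conservative variance (1 + ρ²/2)/(n−3) gives 67.8%.
- Simulated Spearman test at n = 23, bivariate normal data: 69% if .56 is the Pearson correlation, 73% if it is the Spearman correlation.
- Correlation detectable with 80% power at n = 23: tanh((2.170 + 0.842)/√20) = .587 for v = 1, and .600 for v = 1.06. The more conservative variance gives .63.
- At .50, the low end of the plan's own range, power at n = 23 is 56–61%.

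**2. Prevalence of the hypothesis 4 marker.** With 30% mutated and 60% methylated, the silenced share lies between 60% (full overlap) and 90% (no overlap). Under independence it is 1 − (1 − .30)(1 − .60) = 72%. Out of 23 that is 14, 21 and 17 silenced, leaving 9, 2 and 6 unsilenced.

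**3. Power for hypothesis 4.** Normal data, 1.3 SD shift, alpha .03, simulated. The first figure is the exact Wilcoxon test, the second the Spearman t-test on the two-level marker.

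| Split | Meaning | One-tailed | Two-tailed |
|---|---|---|---|
| 8 v 15 | plan's figure | 80% / 82% | 70% / 73% |
| 7 v 16 | mutation at 30% | 77% / 79% | 66% / 69% |
| 14 v 9 | silenced 60% | 81% / 83% | 72% / 75% |
| 17 v 6 | silenced 72% | 72% / 75% | 62% / 62% |
| 21 v 2 | silenced 90% | 34% / 34% | 19% / 19% |

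The first row, one-tailed, reproduces the plan's 80%. With a two-tailed Wilcoxon test, the 8 v 15 split would need a shift of about 1.5 SD to reach 80%.

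**The case against.** Several points on the other side have substance.

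- **The 25-to-23 effect alone is small.** With the method held fixed it costs about 4 points (78.8% to 74.5%, or 76.2% to 71.9%). The rest of the gap comes from using a Spearman rather than a Pearson formula. This stands as a description of size, but Spearman is the test the plan names.
- **The detectable correlation at 23, about .59 to .60, lies inside the plan's .50 to .67.** True, and it is why 23 can be kept. That range was seen for change in Ki-67, though, not for tumor size.
- **One or any of five could mean power for at least one hypothesis.** If two markers were truly associated and independently tested at 72% each, that power would be 1 − .28² = 92%. But the later sentence claims power for the five, both calculations are per-test at .03, and no joint calculation appears. With only one true association, this power is essentially that of the single test.
- **Wilcoxon and Spearman are nearly the same test for a two-level marker.** Agreed. The table shows differences of 0 to 3 points, so the mismatch that matters is in marker and sidedness.
- **The silenced share is uncertain.** The 30% is reported for the PTPR family in the text and for PTPRD or PTPRT in the Figure 5 caption, and no PTPRD methylation rate is given. The 90% case is an extreme and should not carry the argument. At 60%, a one-tailed test keeps slightly more than 80%, so the change of marker need not by itself lose power.

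**Conclusion.** The concern holds: the power statement is wrong as written. At 23 patients and a correlation of .56, power is 74.5% by the formula the plan appears to use and about 72% (68–73%) for the Spearman test it names, a shortfall of roughly 5 to 12 points on four of the five primary tests. For hypothesis 4, the stated 80% is correct only for a one-tailed test of mutation with 8 v 15. For the marker actually tested, at the central 72% prevalence, it is 72–75% one-tailed and 62% two-tailed; at 60% prevalence it is 81–83% and 72–75%.

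These figures assume normal data, alpha .03 for hypothesis 4, and the stated overlap of mutation and methylation. The mismatches in patient number, marker and sidedness do not depend on those assumptions.

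**What to change.** Keep 23 and correct the text.

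1. In 8.2.1, replace the 25-patient sentence with something like: *With 23 evaluable patients, a two-tailed Spearman test at alpha .03 has about 72% power for a true correlation of .56 (68% to 73% across approximations) and 80% power for about .60.*
2. Choose one test and one sidedness for hypothesis 4 and state them identically in 8.2.1 and 8.4.2(4), before any outcome data are examined.
3. Restate the hypothesis 4 power for the mutated-or-methylated marker at its expected split, with the range over plausible overlap, in place of 8 mutated of 23.
4. Say whether the power claim is per hypothesis or for at least one. If the latter, give the calculation.

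The cost is wording in two sections and a less favourable stated power. No extra patients or procedures are needed.
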